#### 6.12.2.4 Days on mechanical ventilation

Mechanical ventilation is defined as subject having 'Intubation and mechanical ventilation' or 'Ventilation + additional organ support – pressors, RRT, ECMO'.

'Days on mechanical ventilation' will be summarized using descriptive statistics (n, mean, standard deviation, median, minimum and maximum) by treatment group.

'Days on mechanical ventilation' will be the number of days on mechanical ventilation up to Day 29. If subject dies early in the study and was on mechanical ventilation at the time of the death then it is assumed that subject was on mechanical ventilation up to Day 29. A sensitivity analysis will be performed assigning the worst possible endpoint score for deaths (i.e., considered to be on mechanical ventilation from baseline up to Day 29 and setting days on mechanical ventilation to 29).

Treatment comparison will be based on analysis of covariance (ANCOVA) model including treatment as a factor, and study site, remdesivir use (No/Yes), dexamethasone use (No/Yes) and WHO Ordinal Scale for Clinical Improvement at baseline as covariates. Treatment difference, standard error, 95% confidence interval and p-value will be presented.

Example SAS codes for the analysis are as follows:

#### 6.12.2.5 All-cause mortality at Day 15, Day 22, and Day 29

The number and percentage for all-cause mortality will be summarized by treatment group and visit.

These endpoints will be analyzed using the same methodology as for the primary endpoint.

Responders are subjects who are alive at the time of the visit.

Non-responders are subjects who died before the visit.

Separate analysis will be performed for each visit.

QMD Ref: Worldwide-TMP-ST-005-7.0 Effective: 12Aug2019	Governing QMD: Worldwide-SOP-ST-001	
Confidentiality Statement		
This document is the property of Worldwide Clinical Trials Inc. and may not be duplicated, copied, altered or removed from company without		
prior approval from Worldwide Quality Assurance or in compliance with Worldwide Standard Operating Procedures		

Worldwide Clinical Trials Controlled Quality Management Document		
WORLDWIDE CLINICAL TRIALS	Sponsor:	Veru Inc.
	Protocol Number:	V0211901
STATISTICAL ANALYSIS PLAN. PHASE 2-3-4		

Responder rates and differences between treatment groups in responder rates will be calculated as sensitivity analysis using the same methodology as for the primary endpoint.

# 6.12.2.6 Proportion of subjects alive and free of respiratory failure at Day 15, and Day 22

These endpoints will be analyzed using the same methodology as for the primary endpoint.

Separate analysis will be performed for each visit.

This will be the same analysis as for primary endpoint but just repeated for days 15 and 22.

# 6.12.2.7 Proportion of subjects alive and discharged from the ICU at Day 15, Day 22, and Day 29

The percentage of subjects alive and discharged from the ICU through Day 15, Day 22 and Day 29 (inclusive) will be summarized.

This analysis will compare the percentage of subjects that are alive and discharged from the ICU (responder) at Day 15, Day 22, and Day 29.

Responders are subjects who are alive and have been discharged from the hospital or not in the ICU at the time of the visit.

Non-responders are subjects who died before the visit or are in the ICU at the time of the visit.

This endpoint will be analyzed using the same methodology as for the primary endpoint.

Separate analysis will be performed for each visit.

# 6.12.2.8 Proportion of subjects alive and discharged from hospital at Day 15, Day 22, and Day 29

The percentage of subjects alive and discharged from the hospital through Day 15, Day 22 and Day 29 (inclusive) will be summarized.

This analysis will compare the percentage of subjects that are alive and discharged from the hospital (responder) at Day 15, Day 22, and Day 29.

Responders are subjects who are alive and have been discharged from the hospital at the time of the visit.

Non-responders are subjects who died before the visit or are in the hospital at the time of the visit.

This endpoint will be analyzed using the same methodology as for the primary endpoint.

QMD Ref: Worldwide-TMP-ST-005-7.0 Effective: 12Aug2019	Governing QMD: Worldwide-SOP-ST-001	
Confidentiality Statement		
This document is the property of Worldwide Clinical Trials Inc. and may not be duplicated, copied, altered or removed from company without prior approval from Worldwide Quality Assurance or in compliance with Worldwide Standard Operating Procedures.		

#### 

Separate analysis will be performed for each visit.

#### 6.12.2.9 Days in ICU

'Days in ICU' will be summarized using descriptive statistics (n, mean, standard deviation, median, minimum and maximum) by treatment group.

'Days in ICU' will be the number of days in ICU up to Day 29. If subject dies early in the study and is in the ICU at the time of the death then it is assumed that subject was in the ICU up to Day 29.

'Days in ICU' will be analyzed using the same methodology as for 'Days in mechanical ventilation' and the same sensitivity analysis will be performed.

#### **6.12.2.10 Days in hospital**

'Days in hospital' will be summarized using descriptive statistics (n, mean, standard deviation, median, minimum and maximum) by treatment group.

'Days in hospital' will be the number of days in hospital up to Day 29. If subject dies early in the study and is in the hospital at the time of the death then it is assumed that subject was in the hospital up to Day 29.

'Days in hospital' will be analyzed using the same methodology as for 'Days in mechanical ventilation'.

6.12.2.11 Proportion of subjects on mechanical ventilation at Day 15, Day 22, and Day 29 The percentage of subjects on mechanical ventilation through Day 15, Day 22 and Day 29 (inclusive) will be summarized.

This analysis will compare the percentage of subjects that are NOT on mechanical ventilation (responder) at Day 15, Day 22, and Day 29.

Responders are subjects who have been discharged from the hospital or are not on mechanical ventilation at the time of the visit.

Non-responders are subjects who died before the visit or are on the mechanical ventilation at the time of the visit.

This endpoint will be analyzed using the same methodology as for the primary endpoint.

Separate analysis will be performed for each visit.

QMD Ref: Worldwide-TMP-ST-005-7.0 Effective: 12Aug2019	Governing QMD: Worldwide-SOP-ST-001	
Confidentiality Statement		
This document is the property of Worldwide Clinical Trials Inc. and may not be duplicated, copied, altered or removed from company without		
prior approval from Worldwide Quality Assurance or in compliance with Worldwide Standard Operating Procedures.		

Worldwide Clinical Trials Controlled Quality Management Document		
WORLDWIDE CLINICAL TRIALS	Sponsor:	Veru Inc.
	Protocol Number:	V0211901
STATISTICAL ANALYSIS PLAN. PHASE 2-3-4		

# **6.12.3** Exploratory Endpoints

#### 6.12.3.1 Area under curve (AUC) of WHO Ordinal Scale for Clinical Improvement

Area under curve (AUC) of WHO Ordinal Scale for Clinical Improvement will be calculated from baseline up to Day 15 using trapezoidal rule. For each subject all available measurements up to study day 15 are included in the calculations. If subject does not have record on Day 15 then the last observation carried forward (LOCF) will be used. If a patient dies on Day 10, then they would be an 8 from Day 10 to Day 15. If the patient is discharged as a 2 on Day 5 then they would be a 2 from Day 5 to Day 15.

Actual collection times will be used in the calculations.

AUC will be summarized by treatment group and listed together with WHO Ordinal Scale for Clinical Improvement.

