8.2 Enrollment

Enrollment should be done after the subject has completed the screening assessments and after it has been determined that the subject meets all the inclusion and exclusion criteria.

Subject will be randomized into one of two treatment groups.

8.3 Day 1

The Day 1 visit assessments will serve as the baseline assessments.

- 1. The medical history should be reviewed and updated to include any changes occurring since the screening visit. This will include the following:
 - a. Number of days from onset of COVID-19 symptoms to Day 1

- b. Specific reason for hospitalization
- 2. Assessment of eligibility
- 3. Vital signs (temperature/pulse/supine, if possible, blood pressure)
- 4. SpO_2
- 5. Physical examination (including weight)
- 6. Chest X-ray or Computed Tomography (CT) scan
- 7. Clinical Laboratory Tests
 - a. Hematology (Appendix A)
 - b. Serum chemistry (Appendix A)
 - c. Urinalysis
- 8. Record the usage of any concomitant medications and ongoing treatments.
- 9. Adverse events (ongoing on Day 1)
- 10. First dose of study drug
- 11. Temperature and SpO₂ every 12 hours after dosing

8.4 Day 2 through Day 21

The following assessments will be conducted on each of Day 2 to Day 21

- 1. Temperature and SpO₂ every 12 hours
- 2. Vital signs (temperature/pulse/supine, if possible, blood pressure)
- 3. Record the usage of any concomitant medications and ongoing treatments. This should include the following:
 - a. Documentation of the standard of care
 - b. The clinical rationale for initiation of mechanical ventilation, if necessary
 - c. Documentation of supportive measures for ARDS (e.g., proning, paralytics, etc.)
 - d. Care decisions that are based on limitations of resources at the clinical site
- 4. Adverse events
- 5. Dose study drug
- 6. At the time of discharge from the hospital, patients should be advised to use refrain from prolonged exposure to the sun or use at least SPF 50 on all exposed skin and protective clothing during prolonged sun exposure until the Day 60 adverse event assessment.

8.5 Day 3, Day 9, and Day 15

The following additional assessment will be conducted on Days 3, Day 9 and 15:

- 1. Serum Chemistry (Appendix A)
- 2. Hematology (Appendix A)
- 3. Assessment of primary and secondary endpoints (Day 15 only)
- 4. Physical examination (including weight) (Day 15 only)
- 5. 12 lead ECG (single) (Day 15 only)
- 6. Pregnancy test (Day 15 only)

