9.4.1 Secondary Endpoints

9.4.1.1 Mean change from baseline in WHO Ordinal Scale for Clinical Improvement at Day 15, Day 22 and Day 29

The mean change in WHO Ordinal Scale for Clinical Improvement from baseline to Day 22 and from baseline to Day 29 will be assessed.

The worst category recorded on Day -1 will be baseline and the worst category recorded on Day 22 and Day 29 of the study will be used in this analysis.

Descriptive statistics (n, mean, standard deviation, median, minimum and maximum) will be summarized for absolute values, and change from baseline by treatment group and visit.

Change from baseline will be analyzed using mixed model for repeated measures (MMRM) including treatment, visit and treatment-by-visit interaction as fixed effects and study site and WHO Ordinal Scale for Clinical Improvement at baseline as covariate. The resulting F-tests will be based on Kenward-Roger's adjusted degrees of freedom. Least squares means, standard errors, 95% confidence intervals and p-values for treatments and treatment differences at each visit will be presented.

9.4.1.2 Proportion of subjects that are Grade 5, 6, 7, or 8 on the WHO Ordinal Scale for Clinical Improvement at Day 15, Day 22, and Day 29

Proportion of subjects that are Grade 5, 6, 7, or 8 on the WHO Ordinal Scale for Clinical Improvement at Day 15, Day 22, and Day 29 will be assessed. This analysis will compare the percentage of subjects that have NOT progressed to a WHO Ordinal Scale for Clinical Improvement score of 5, 6, 7, or 8 (responder) on Day 15, Day 22 or Day 29. The worst category on each day of the study will be used in this analysis. The percentage of subjects that meet these criteria in each of the two treatment groups will be summarized and compared observationally and statistically.

This endpoint will be analyzed using the same methodology as for the primary endpoint.

9.4.1.3 Proportion of subjects with normalization of fever and oxygen saturation through Day 15, Day 22, and Day 29.

The percentage of subjects with normalization of fever and oxygen saturation through Day 15, Day 22 and Day 29 (inclusive) will be summarized. A subject will be considered as a treatment success if fever normalization maintained for at least 24 hours AND peripheral capillary oxygen saturation (SpO₂) >94% sustained for 24 hours is observed.

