12.2 Appendix B: Schedule of Study Evaluations

Day	Screen ^a	Day 1	Days 2-21	Days 3, 9, & 15	Day 16	Days 22 ^d and 29	Days 45 and 60
Informed Consent and	Х						
HIPAA							
Medical History	Х	Х					
Assessment of Eligibility	Х	Х					
Physical Exam	Х	Х		Xf		Х	
Vital signs	Х	Х	Х			Х	
Pregnancy test (female	Х		Xf			X ^g	
subjects only)				0			
12-lead ECG (single)	Х			X ^t		X	
Chest X-ray or CT		Х				Х	
Clinical Laboratory Tests							
Hematology	Х	Х		Х		Х	
Urinalysis	Х	Х				Х	
Serum Chemistry	Х	Х		Х		Х	
Temperature/SpO ₂	Х	Х	Xe			Х	
Dosing ^{b,c}		Х	Х				
Pharmacokinetic assessment				X ^{h, f}	X ^h		
Assessment of primary and secondary efficacy endpoints				\mathbf{X}^{f}		Х	Х
Assessment of conmeds	Х	Х	Х			Х	
Assessment of AEs		Х	Х			Х	X

a Screening evaluations are to be conducted within 2 days prior to Day 1.

b Subjects will be treated for 21 days OR until discharged from hospital

c Subjects can be discontinued if they are not responding to therapy d Early termination assessments the same as Day 22 assessments

e Temperature and SpO₂ will be taken every 12 hours on these days

f Day 15 only g Day 29 only

h Plasma samples for pharmacokinetic assessment will be taken at baseline (prior to dosing on Day 15) and at 4 hours (±2 hours), 12 hours (±2 hours) after dosing on Day 15, and at 24 hours (±2 hours) after dosing on Day 15 (prior to dosing on Day 16).

PROTOCOL SIGNATURE PAGE

Protocol Number:	V0211901
Protocol Date:	FINAL Amendment 6 (Version 7)/ 25 September 2020
Protocol Title:	Randomized, Placebo-Controlled, Phase 2 Study of VERU-111 for the Treatment of Severe Acute Respiratory Syndrome Coronavirus 2 (SARS-CoV-2) in Patients at High Risk for Acute Respiratory Distress Syndrome (ARDS).

SIGNATURE:

Sponsor

Date

Name and Title of Sponsor Representative

This signature of the Sponsor Representative constitutes approval of this protocol.

PRINCIPAL INVESTIGATOR SIGNATURE PAGE

Protocol Number:	V0211901
Protocol Title:	Randomized, Placebo-Controlled, Phase 2 Study of VERU-111 for the Treatment of Severe Acute Respiratory Syndrome Coronavirus 2 (SARS-CoV-2) in Patients at High Risk for Acute Respiratory Distress Syndrome (ARDS).
Protocol Date:	FINAL Amendment 6 (Version 7)/ 25 September 2020

SIGNATURE:

Principal Investigator:

Date

Name of Principal Investigator (Please Print)

Address of Principal Investigator

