#### 6.2.1 Baseline

Baseline is defined as the last non-missing value (either scheduled, unscheduled or repeat) before the subject receives the first dose of study drug.

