#### **6.12.2** Secondary Endpoints

# 6.12.2.1 Change in mean WHO Ordinal Scale for Clinical Improvement at Day 15, Day 22 and Day 29

The mean change in WHO Ordinal Scale for Clinical Improvement from baseline to Day 15, Day 22 and Day 29 will be assessed.

Baseline for WHO Ordinal Scale is the last available record up to and including Day 1. If subject died or was discharged from the hospital prior to Day 15, 22 or 29 and WHO Ordinal Scale for Clinical Improvement is not collected or record is otherwise missing at those timepoints then the last available observation before or at the time of death/discharge will be carried forward.

Analysis will be performed using two different approaches, including the LOCF values and excluding LOCF values. Further, these analyses will be repeated using separate baseline definition. As the time of WHO Ordinal Scale is collected it cannot be definitely confirmed if Day 1 record was taken before or after start of study treatment. Sensitivity analysis will be performed using the WHO Ordinal Scale from Screening record.

Descriptive statistics (n, mean, standard deviation, median, minimum and maximum) will be summarized for absolute values and change from baseline by treatment group and visit.

Change from baseline will be analyzed using mixed model for repeated measures (MMRM) including treatment, visit and treatment-by-visit interaction as fixed effects, and study site, remdesivir use (No/Yes), dexamethasone use (No/Yes) and WHO Ordinal Scale for Clinical Improvement at baseline as covariates. The resulting F-tests will be based on Kenward-Roger's adjusted degrees of freedom. Subject effect will be assumed to be random and an unstructured covariance structure will be used for within subject variation. If this model does not converge then the following covariance matrices will be used in order until the model converges: Toeplitz, first-order autoregressive, and compound symmetry. Least squares means, standard errors, 95% confidence intervals and p-values for treatments and treatment differences at each visit (study days 15, 22, 29, 45 and 60) will be presented.

QMD Ref: Worldwide-TMP-ST-005-7.0 Effective: 12Aug2019 Governing QMD: Worldwide-SOP-ST-0		
Confidentiality Statement		
This document is the property of Worldwide Clinical Trials Inc. and may not be duplicated, copied, altered or removed from company without		

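### The WHO-scale AUC starts at each subject's own baseline date and is not divided by its duration, so a subject with no Day 1 score accrues up to two extra days of area for the same illness

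*SAP*

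**What the plan says.** SAP 6.12.3.1 lists the AUC of the WHO Ordinal Scale as an exploratory endpoint. It "will be calculated from baseline up to Day 15 using trapezoidal rule". On the time axis it adds: "Actual collection times will be used in the calculations". On the scores that enter: "For each subject all available measurements up to study day 15 are included in the calculations". A missing Day 15 score is carried forward. A death counts as 8 from its own day to Day 15, and a discharge score is held from its own day to Day 15. No division by the length of the curve is mentioned. The AUC is to be summarised by arm and listed; no test or model is given.

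The starting point comes from elsewhere. SAP 6.12.2.1 says: "Baseline for WHO Ordinal Scale is the last available record up to and including Day 1". The general rule in SAP 6.2.1 is stricter: "Baseline is defined as the last non-missing value (either scheduled, unscheduled or repeat) before the subject receives the first dose of study drug". Section 6.12.3.1 does not say which applies; I take the scale-specific one. A footnote to Protocol Appendix B gives the earliest date: "Screening evaluations are to be conducted within 2 days prior to Day 1".

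SAP 6.2.9 says that only scheduled post-baseline values are tabulated, and that repeat and unscheduled ones are disregarded apart from listings.

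**The concern.** An undivided AUC is a score multiplied by time, so subjects are comparable only if all are observed over the same span. Here the right-hand end is fixed at Day 15, by carry-forward if necessary, but the left-hand end is wherever the subject's baseline record lies. Two subjects with the same course can differ only because one was last scored before treatment at screening and the other on Day 1. The difference looks like extra illness, although the added days precede the first dose. At stake is whether the arm summaries of this endpoint can be read as burden over the first 15 days.

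A second, lesser matter is that the section takes every available score, while 6.2.9 sets unscheduled scores aside. Two programmers could follow the text and build different curves.

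**Working it through.** The documents state no AUC value, so there is no figure to reproduce. The score paths below are my assumptions, for illustration.

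**Inputs**
- Time axis: with study day as defined in SAP 6.2.2, Day 1 is t = 0, Day 15 is t = 14, Day -1 is t = -1 and Day -2 is t = -2. I count in whole days.
- Earliest start: Day -2 (Protocol Appendix B).
- Rule: AUC = sum of (t2 - t1) × (s1 + s2) / 2 over successive records (SAP 6.12.3.1).

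**Unchanged score of 4**

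| Baseline record | Days covered | AUC | Against Day 1 start | AUC / duration |
|---|---|---|---|---|
| Day 1 | 14 | 4 × 14 = 56 | – | 4.0 |
| Day -1 | 15 | 4 × 15 = 60 | 15/14 = 1.071, +7.1% | 4.0 |
| Day -2 | 16 | 4 × 16 = 64 | 16/14 = 1.143, +14.3% | 4.0 |

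The percentages are the same at any constant score; for example, a score of 5 gives 70, 75 and 80.

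**Straight line from 4 at baseline to 2 on Day 15**
- The mean score is 3, so the AUC is 3 × 14 = 42, 3 × 15 = 45 or 3 × 16 = 48.
- The excess is again 7.1% or 14.3%, and division by duration gives 3.0 each time.

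**The SAP's discharge example (score 2 from Day 5), with an assumed baseline of 4 and no score between**
- Start Day 1: 4 × 3 + 10 × 2 = 32.
- Start Day -2: 6 × 3 + 10 × 2 = 38, and 38/32 = 1.19.
- Divided by duration: 32/14 = 2.29 and 38/16 = 2.38.
- So 14.3% is the maximum for an unchanged score but not for every course. Division by own duration shrinks the difference here without quite removing it. Placing the baseline score at Day 1 gives 32 in both cases.

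**Effect on an arm mean**
- The plan is 20 subjects per arm. The number without a Day 1 score is not given, so I assume k in one arm and none in the other.
- Each such subject, at a constant 4 and a Day -2 baseline, adds 64 - 56 = 8 units, so the arm mean moves by 8k/20 = 0.4k.
- For k = 1 to 5 this is 0.4 to 2.0 units on 56, or 0.7% to 3.6%.

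**The case against.** The strongest reply is that the start may hardly ever float. The WHO baseline admits Day 1, and SAP 6.12.2.1 worries about whether a Day 1 score came before or after the first dose, not about its absence. If every subject has a Day 1 score, every curve starts at Day 1 and the problem is empty. The shift is limited to 2 days, nothing suggests that missing Day 1 scores depend on arm, and the endpoint is exploratory, with no test. All of this stands and keeps the point small. It does not remove the defect, because the rule as written gives unequal areas for equal illness whenever a Day 1 score is absent.

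A reader might go further and infer that the AUC merely joins a baseline score to a Day 15 score, so that ventilation between visits is missed. The basis would be Protocol 8.5, where the entry for Days 3, 9 and 15 reads "Assessment of primary and secondary endpoints (Day 15 only"), together with Appendix B, which lists no other endpoint assessment between Day 1 and Day 15. The documents do not support that inference:
- SAP 6.12.3.1 takes all available scores and places death and discharge on their own days.
- The schedule is not a full record of scoring. It shows no endpoint assessment at screening or Day 1, yet SAP 6.12.2.1 uses WHO scores from both.
- SAP 6.12.2.4 defines mechanical ventilation by the scale's grade 6 and 7 descriptors and counts days in that state to Day 29, which suggests dated category records between visits.
- Protocol 9.4.1.2 says: "The worst category on each day of the study will be used in this analysis". This is ambiguous but compatible with daily recording.

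Only if no intermediate score existed would a subject at 4 on Days 1 and 15, with grade 6 on Days 4-11, get 56 where daily scores give 56 + 2 × 8 = 72. That is conditional on something the documents leave open. Ventilation days are in any case a separate endpoint. Replacing the trapezoid with held scores would be largely a matter of preference.

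**Conclusion.** The point holds for the time base. Under the stated rule, a subject whose WHO baseline predates Day 1 accrues 15 or 16 days of area instead of 14, which is 7% or 14% too much for an unchanged score. This rests on three readings: the baseline definition in 6.12.2.1 governs the AUC, the screening score can be up to 2 days old, and no division by duration is intended because none is stated. It affects only subjects without a Day 1 score. Their number is not given, and no bias between arms is shown. For an exploratory, descriptive endpoint the consequence is minor, but the correction is nearly free. The tension between 6.12.3.1 and 6.2.9 is a wording matter to settle at the same time. I do not conclude that the AUC rests on two scores or that it misses ventilation.

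**What to change.** In SAP 6.12.3.1:

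1. Place the baseline score at Day 1 (t = 0) for every subject, whatever its collection date, and use actual times only after that. Alternatively, report the AUC divided by its own duration, as a time-weighted mean score. The Day 1 anchor is the cleaner choice: it equalises every course in the working, whereas division is exact for constant and straight-line courses only. With the anchor in place, dividing by 14 gives the mean score from Day 1 to Day 15.
2. Name the baseline definition that applies (6.12.2.1 or 6.2.1).
3. State that every dated WHO record between Day 1 and Day 15 enters the AUC, as an explicit exception to 6.2.9, and name the source of those records.

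The cost is a few sentences in the SAP and a minor change to the program for Table 14.2.2.9. No new data are needed.
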